The results of randomized controlled trials (RCTs) of rTMS for PTSD have also been promising. In a double-blind, sham-controlled RCT, Cohen et al. examined the efficacy of 14 days of rTMS over the right DLPFC, comparing low frequency (1 Hz) to high frequency (10 Hz) in 24 patients with PTSD (61). Results indicated significant improvement in core PTSD symptoms for patients in the 10 Hz treatment group compared to sham, but not the 1 Hz group. Boggio et al. conducted a double-blind, sham-controlled RCT in 30 patients diagnosed with PTSD (62). Patients were randomized to either sham or high frequency (20 Hz) rTMS for two weeks, over right or left DLPFC. Results showed that both right and left 20 Hz rTMS significantly reduced PTSD symptoms, but the effect was slightly larger on the left side. The reduction in PTSD symptoms was still present at 3-month post-treatment follow-up. Only one study by Osuch et al. examined the effects of rTMS in combination with psychotherapy (63). In a sham-controlled, cross-over study design, 9 patients were randomized to low frequency (1 Hz) or sham rTMS to the right DLPFC rTMS in conjunction with imaginal exposure therapy. Results showed no effect for 1 Hz rTMS compared to sham, but the small sample size likely led to a Type II error. Finally, Watts et al. conducted the most recent sham-controlled RCT of 20 patients with PTSD randomized to sham or right DLPFC low frequency 1 Hz rTMS over 10 sessions, and found significant improvement in PTSD and depressive symptom scores in the active group over the sham, and this change sustained up to 2 months post-rTMS (64).

The results of these studies suggest that rTMS targeting the right DLPFC can ameliorate symptoms of PTSD, but there are discrepant results about the efficacy of low frequency (1 Hz) vs. high frequency (10-20 Hz). Subjects tolerated the procedure well with no cognitive dysfunction and low dropout rates. Furthermore, the utility of rTMS in conjunction with other therapies such as psychotherapy is unclear, given the one small study to date.

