In Canada, there are no restrictions for the range of mental disorders that rTMS can be used for in treating patients, although MDD is the condition that is the most commonly treated. Based on reports in the literature, we anticipate that right sided rTMS is as safe and tolerable as left-sided rTMS. Therefore, we propose to conduct a study of rTMS in patients with PTSD who are starting the group psychotherapy program at VGH. Since previous research has shown a discrepancy between the efficacy of high versus low frequency rTMS on the symptoms of PTSD, we will examine the use of high (10 Hz) versus low (1 Hz) frequency rTMS delivered over the right DLFPC of patients suffering with PTSD symptoms unrelated to combat. Standardized evaluations will be done to assess for clinical improvements in the PTSD, depressive and anxiety symptom clusters, and for tolerability with monitoring of adverse events and dropout rates.

Primary Hypothesis

The primary hypothesis is that high frequency (10 Hz) rTMS over the right DLPFC will be superior to low frequency (1 Hz) in reducing scores as measured by the PTSD Check List.

Research Method

Subject Recruitment

Subjects will be recruited from the PTSD treatment program conducted at the VGH Outpatient Psychiatry Program (OPP). Mid-way during the Phase 1 of the group psychoeducational program, patients will be approached regarding their willingness to participate in the study. Those subjects expressing interest will receive a description of the study along with an informed consent form that the client can sign if s/he chooses to participate. Should the patient agree to participate, a screening interview will be administered to determine if s/he meets the inclusion / exclusion criteria.

Inclusion criteria: (1) primary diagnosis of PTSD as determined by a structured interview (Mini International Neuropsychiatric Interview, MINI (68)); (2) no change in psychotropic medications within 4 weeks before the start of rTMS; (3) age greater than 19 years and less than 70 years; and (4) competent to give informed consent.

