Exclusion criteria: (1) any non-fixed metal object or implant (including cochlear implants) in brain, skull, scalp, or neck within 30 cm of the magnetic rTMS coil; (2) implantable devices, including cardiac pacemakers and defibrillators; (3) other contraindications to rTMS, including history of seizures (except childhood febrile seizures) or recurrent and unexplained syncope, first degree relative with a history of epilepsy, treatment with a medication known to substantially decrease the seizure threshold, and pregnancy; (4) psychiatric diagnoses of psychosis or psychotic disorder (including psychotic depression), bipolar type 1 disorder, organic mental disorders; (5) substance abuse/dependence within the past 3 months; (6) active suicidal risk as judged by the clinician; (7) borderline or antisocial personality disorder; (8) acute medical illness, including cancer; (9) any significant central nervous system disorder such as brain mass, stroke.

Research Design

This will be a prospective, 2-week, double-blind (subject and evaluator) randomized controlled pilot study to assess the effect of repetitive transcranial magnetic stimulation (rTMS) in patients with a confirmed diagnosis of PTSD. The rTMS will target the right DLPFC. Subjects will be randomized into either 1 Hz or 10 Hz treatment arms, or sham arm.. The rTMS will be administered between Phase 1 and 2 of the PTSD OPP, so there will not be concurrent group therapy during the 2-week rTMS sessions. Outcome measures will be assessed at baseline, after 1 week and 2 weeks (completion) of rTMS, and at follow up after Phase 2 of the PTSD OPP group psychotherapy program (approximately 10 weeks after completion of rTMS).

Primary Outcomes

 Changes in PTSD symptoms as measured by – Clinician Administered PTSD Scale (CAPS (69)), patient rated Post Traumatic Stress Disorder Checklist Civilian (PCL-C).

Secondary Outcomes

- Changes in symptoms as assessed by:
 - For Depression clinician administered Hamilton Depression Rating Scale (17 items) (HAMD), patient rated Quick Inventory of Depressive Symptomatology-Self-report (QIDS-SR (70)).
 - For Anxiety Beck Anxiety Inventory (BAI), Generalized Anxiety Disorder Assessment (GAD-7).
 - These are all standardized, validated symptom measures that are widely used in clinical and research settings. The QIDS-SR, GAD-7 and PCL-C are also used as routine clinical outcome measures in the PTSD OPP.
- Adverse events, safety, and tolerability

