The motor threshold is determined during the first session by applying TMS over the motor cortex in order to get the minimal level of stimulus intensity from the device which will create a contraction in the contralateral abductor pollicis brevis muscle of the thumb. The DLPFC will be targeted by measuring 6 cm anterior to this motor cortex landmark, along the sagittal plane, as the patient will be wearing a swimmer's cap. The intensity of the stimulus is set by going 100-120% of the intensity which determined motor threshold. rTMS therapy over the right DLPFC will be given on 5 consecutive days every week for two weeks for a total of 10 therapy sessions using a Magstim Super Rapid2 (Magstim Company Ltd., Carmarthenshire, Wales, UK) with a Rapid-2 Air Film Coil.

Subjects will receive either active rTMS to the right side at 1 Hz or at 10 Hz, or sham treatment for 37.5 minutes per session. The stimulus parameters that will be chosen for treating subjects will be similar to the parameters currently used at our clinic to stimulate patients with depression. A clinic nurse will always be present to deliver the treatment, and a supervising rTMS psychiatrist will oversee the appropriate placement and intensity of the coil, as well as responding to any adverse event which may arise. Each subject is given appropriate ear protection due to the intensity of the sound from each treatment pulse delivered by the device. Subjects who experience some initial discomfort during the session, such scalp or facial irritation, will prompt trying a different orientation of the coil at the same DLPFC site, which will usually relieve the discomfort. Subjects may leave immediately on their own after the treatment is completed, and may even drive, unless a serious adverse event occurred.

SAMPLE SIZE

Based on the standardized effect size for the primary outcome, the PTSD Check List, as determined by the previous RCT (71;72) (d=1.4), and with alpha set to 0.05 and 80% power, we estimated a sample size of nine subjects/condition. Note that this effect size is regarded as a large effect and is clinically significant.

Data Analysis

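### Does the 80% power fail for the primary comparison of 10 Hz with 1 Hz because the arms behind d=1.4 are not named?

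*Combined protocol and SAP*

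**What the plan says.** The Sample Size section takes a standardized effect on the PTSD Check List "as determined by the previous RCT (71;72) (d=1.4), and with alpha set to 0.05 and 80% power" and arrives at nine subjects per condition. It speaks of one trial but gives two references, and it states neither the arms compared, nor the type of score (endpoint, change or adjusted), nor whether alpha is two-sided.

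The Primary Hypothesis is that "high frequency (10 Hz) rTMS over the right DLPFC will be superior to low frequency (1 Hz", judged on that same scale. The Research Design section adds a sham arm and describes the trial as a "randomized controlled pilot study to assess the effect of repetitive transcranial magnetic stimulation (rTMS". The Data Analysis section plans ANCOVA adjusted for baseline.

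In the reference list, 71 and 72 are the same papers as 61 and 62, both of which the background describes. The first is a sham-controlled trial "comparing low frequency (1 Hz) to high frequency (10 Hz) in 24 patients with PTSD"; it found "significant improvement in core PTSD symptoms for patients in the 10 Hz treatment group compared to sham, but not the 1 Hz group". Of the second, the background says: "Patients were randomized to either sham or high frequency (20 Hz) rTMS for two weeks". A further trial (reference 64) had "20 patients with PTSD randomized to sham or right DLPFC low frequency 1 Hz rTMS over 10 sessions". On its outcome, the background reports that the investigators "found significant improvement in PTSD and depressive symptom scores in the active group over the sham".

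**The concern.** A power statement holds for one comparison. A reader will attach this one to the Primary Hypothesis, yet the background reports the results of both cited trials against sham. The 20 Hz trial, as described, has neither a 1 Hz nor a 10 Hz arm, so it cannot have yielded a 10 Hz versus 1 Hz effect.

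If 1.4 is an active-versus-sham effect, using it for 10 Hz versus 1 Hz treats 1 Hz as no better than sham. Part of the background points that way, but the 20-patient trial of right-sided 1 Hz points the other way, and the protocol gives these conflicting results as its reason for studying frequency. Any true 1 Hz benefit would come straight off the difference being tested. The stake is a trial presented as 80% powered that might have much less power for its main question, and a null result that might be read as showing the two frequencies to be equal.

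**Working it through.** **Inputs.** d = 1.4, alpha 0.05, power 80%, n = 9 per arm (Sample Size); three arms (Procedures and Methods); ANCOVA on baseline (Data Analysis). Two-sided testing is an assumption, checked in step 2. The documents give no baseline-endpoint correlation r, so every value of r below is assumed.

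**1. The plan's figure.** n per arm = 2(z₀.₉₇₅ + z₀.₈₀)² / d² = 2(1.960 + 0.842)² / 1.4² = 8.01, rounded up to 9. The plan's number is reproduced.

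**2. Sidedness.** The one-sided version of the formula gives 7, and a one-sided t-test needs 8. Nine fits a two-sided test.

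**3. Exact power at nine per arm.** The noncentrality is d√(n/2) = 1.4 × √4.5 = 2.97, with 16 degrees of freedom and a critical value of 2.12. Power is 79.6%. (The normal approximation gives 84.4% at n = 9; a strict t-test would need 10 per arm to pass 80%.) The shortfall of 0.4 percentage points is immaterial. The formula takes only the size of the difference, so the result applies to any two arms that differ by 1.4 SD.

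**4. If the true 10 Hz versus 1 Hz difference is smaller.** Same t-test, with assumed differences. The second column is the 1 Hz benefit over sham that would produce each one if 10 Hz versus sham were exactly 1.4 SD.

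| Difference (SD) | Implied 1 Hz benefit (SD) | Power |
|---|---|---|
| 1.4 | 0 | 79.6% |
| 1.2 | 0.2 | 66.7% |
| 1.0 | 0.4 | 51.3% |
| 0.7 | 0.7 | 28.7% |

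**5. The planned ANCOVA.** Adjustment reduces the residual variance, but by how much depends on the scale of the 1.4. Relative to the endpoint variance the residual fraction is 1 − r². Relative to the variance of change, 2σ²(1 − r), it is (1 − r²) / [2(1 − r)] = (1 + r)/2. With three arms, 23 error degrees of freedom and power averaged over chance baseline imbalance:

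| r (assumed) | Scale of d | Residual fraction | Power at 1.4 | Difference for 80% power | 1.4 minus that |
|---|---|---|---|---|---|
| 0.3 | endpoint SD | 0.91 | 83% | 1.34 | 0.06 |
| 0.3 | change SD | 0.65 | 93% | 1.14 | 0.26 |
| 0.5 | either | 0.75 | 89% | 1.22 | 0.18 |
| 0.6 | endpoint SD | 0.64 | 93% | 1.13 | 0.27 |
| 0.6 | change SD | 0.80 | 87% | 1.26 | 0.14 |

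The last column is the largest 1 Hz benefit over sham that still leaves 80% power. It runs from 0.06 to 0.27 SD, and its ordering in r reverses with the scale of d. The Data Analysis section defines the endpoint as change, so the change scale is at least as natural a reading as the endpoint scale. The documents fix neither r nor the scale, so no single restated power can be derived from them.

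**6. Could 1.4 be a 10 Hz versus 1 Hz effect?** Yes. The 24-patient trial (reference 71) included both frequencies. The protocol neither says that this is the source nor rules it out.

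**The case for a change.** The strongest case for a change is that power for the main hypothesis should not quietly assume the answer to the question under study. The finding that 1 Hz did not beat sham is a non-significant result in a 24-patient trial. The nine-patient cross-over trial that also saw no 1 Hz effect is put down by the protocol itself to a likely Type II error. Against these stands a positive 20-patient trial of 1 Hz on the same side. A 1 Hz benefit of only 0.4 SD would leave about 51% power unadjusted, or 63% with ANCOVA at an assumed correlation of 0.5. The pilot label does not remove the 80% claim, and one rewritten paragraph would cure the ambiguity at almost no cost.

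Some of this stands. The arms and score type behind 1.4 are missing, and one of the two references cannot support the primary comparison. A reader is entitled to treat the 80% as conditional. What does not follow is that a stated figure is missed: every lower power rests on an assumed 1 Hz benefit, and most also on an assumed correlation and scale. Writing such figures into the protocol would replace an undocumented input with several others. The risk of reading a null result as equality is present in any trial with nine per arm and is met by cautious reporting. A fuller citation would not remove it.

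**Conclusion.** No change is called for. The arithmetic is right: nine per condition gives 79.6% power by two-sided t-test for a true difference of 1.4 SD between any two arms. The 80% is undocumented for 10 Hz versus 1 Hz but not shown to be wrong, and it stands if 1.4 came from the two frequency arms of reference 71. If 1.4 is instead an effect against sham, power for the primary comparison depends on a 1 Hz benefit, a baseline correlation and a score scale that the documents do not give; the 29% to 67% at assumed differences of 0.7 to 1.2 SD illustrates this and does not estimate it.

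The missing detail is the provenance of one planning input. Supplying it would leave the number of subjects, the randomization, the ANCOVA and the two-week endpoint as they are, and the stated power plays no part in the analysis. For a pilot, the sensible reading is that the study can detect a difference of about 1.4 SD, whichever pair of arms is compared.

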 - Incidence of serious and non-serious adverse events attributable to rTMS (eg: headache, scalp pain, facial pain, dizziness, tinnitus, light-headedness, syncope, seizure).
 - Montreal Cognitive Assessment (MOCA).

Procedures and Methods

After giving written, informed consent, subjects will undergo baseline assessment measures. Eligible subjects will be randomized to one of three treatment arms (high or low frequency rTMS, or sham rTMS). Concealment of allocation will be accomplished using a computerized randomization program that reveals treatment allocation only after the unique subject identifier is entered. The randomization codes will be available on a 24-hour basis in the (unlikely) event that the blind needs to be broken for clinical reasons. The subject will be blind to treatment condition because they will be unaware of the rTMS frequencies or sham condition used in the study. The rTMS nurse will be unblinded, but the

evaluator for clinician-rated assessments will be blind to treatment conditions. The rTMS nurse will not interact with the evaluator, and should any unblinding occur, the evaluator will be replaced.

The secondary outcome measures will be repeated weekly after rTMS session number 5 and 10 (or at termination, for early withdrawals). Adverse events and severity (mild, moderate, severe) will be recorded at each session. Serious adverse events will be defined according to standard Health Canada definitions as those which: a) result in death; b) are life threatening; c) are severely or permanently disabling; d) require inpatient hospitalization; e) result in an incidence of cancer; f) result in a drug overdose or reaction after drug withdrawal. All subjects who withdraw from the study will be asked to state a reason for withdrawal. The outcome measures will also be repeated after completion of the Phase 2 group psychotherapy program (about 10 weeks following completion of the rTMS).

The blind evaluator(s) will receive standardized training to establish inter-rater reliability using videotaped interviews. Reliability of outcome assessment will also be enhanced by using structured interview guides for the HAMD and CAPS.

Interventions (rTMS Stimulation)

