All randomized subjects will be included in the analysis based on intent-to-treat. Missing data will be imputed using last observation carried forward (LOCF). The pre-specified primary efficacy endpoint is the adjusted mean change from baseline to endpoint (2 weeks) on the PTSD Check List using LOCF. All comparisons will be analyzed using ANCOVA adjusting for baseline value. The secondary outcomes will also be analyzed using a similar analysis, when appropriate. Post hoc analyses will also rTMS & PTSD Protocol V3.0 6

examine observed case data. Categorical data (such as proportions of the sample with adverse events) will be analyzed using chi-square tests or Fisher's test where cell sizes warrant.

Reference List

- (1) APA. American Psychologic Association. Diagnostic and statistical manual of mental disorders . 4 ed. Washington, DC: APA; 1994.

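### LOCF on the primary 2-week PTSD Check List lets a baseline, week 1 or termination score stand in for week 2, and no week 2 score is expressly sought from subjects who stop early

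*Combined protocol and SAP*

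**What the plan says.** The Data Analysis section sets the analysis population: "All randomized subjects will be included in the analysis based on intent-to-treat". It then gives a general rule, "Missing data will be imputed using last observation carried forward (LOCF", and builds that rule into the endpoint: "The pre-specified primary efficacy endpoint is the adjusted mean change from baseline to endpoint (2 weeks) on the PTSD Check List using LOCF". The model is ANCOVA adjusted for baseline. The only other treatment of missing data is a post hoc analysis that will "examine observed case data".

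Two sections bear on which scores exist to be carried forward:

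- Research Design: "Outcome measures will be assessed at baseline, after 1 week and 2 weeks (completion) of rTMS", with a follow-up after Phase 2. It does not mention early withdrawals. The PCL-C is listed under Primary Outcomes.
- Procedures and Methods: "The secondary outcome measures will be repeated weekly after rTMS session number 5 and 10 (or at termination, for early withdrawals". This names only the secondary measures. It adds "All subjects who withdraw from the study will be asked to state a reason for withdrawal" and, for the later visit, "The outcome measures will also be repeated after completion of the Phase 2 group psychotherapy program".

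No section says whether the PCL-C is taken at termination, or at week 2 from someone who has already stopped.

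**The concern.** LOCF treats a subject's last available score as the week 2 score. For someone who leaves before session 5, that score may be the baseline, so the analysis records no change. For someone who leaves later, it is a week 1 or part-treatment score. Whether this is right depends on how leavers would have scored at week 2, and the planned data cannot show that. The observed-case analysis makes the opposite assumption, that leavers would have done as completers did.

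With nine subjects per condition, each is 1/9 = 11% of an arm, so a few carried scores on one side can move the primary comparison of 10 Hz with 1 Hz. The general LOCF sentence is also not limited to week 2. If it covers the follow-up visit, a score from before Phase 2 would be carried across a programme that the background expects to have more effect than Phase 1.

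**Working it through.** **The plan's own figure.** Inputs from the Sample Size section: d = 1.4, alpha 0.05 (two-sided assumed), 80% power. Then n = 2 × ((1.960 + 0.842)/1.4)² = 8.01, rounded up to 9 per condition. By the noncentral t, power at 9 per arm is 79.6%. The figure reproduces. The section states no dropout allowance.

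**Assumed inputs.** The documents give no dropout rate and no week 1 effect, so these are assumptions, in SD units:

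- p: expected share of the 10 Hz arm lost (1 Hz complete)
- f: share of the week 2 change already in the carried score (0 = baseline, 0.5 = week 1, 0.25 = an early termination score)
- m: improvement common to all arms
- δ: extra improvement on 10 Hz

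Expected LOCF difference = (m + δ) × [1 − p(1 − f)] − m. Positive values favour 10 Hz.

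**True benefit: δ = 1.4, m = 0, p = 2/9.** With baseline carried, LOCF gives 1.4 × 7/9 = 1.09.

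- Case A, leavers would improve as completers do. The intent-to-treat effect is 1.40. LOCF is 0.31 too low; observed cases give 1.40, correct.
- Case B, leavers keep no benefit. The intent-to-treat effect is 1.4 × 7/9 = 1.09. LOCF is correct; observed cases give 1.40, 0.31 too high.
- With week 1 carried, LOCF gives 1.4 × (1 − 2/9 × 0.5) = 1.24, which is 0.16 too low in A and about 0.15 too high in B.

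LOCF returns the same 1.09 in A and B although the truths differ by 0.31. A measured week 2 score returns 1.40 in A and 1.09 in B.

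**No true difference: δ = 0.** The expected false difference is −p(1 − f)m, taking leavers to improve anyway. Type I error is from ANCOVA simulation (three arms of 9, baseline correlated 0.6 with later scores, half the change by week 1, 40,000 runs per scenario).

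| Loss from 10 Hz | Score carried | m | False difference | Type I error |
|---|---|---|---|---|
| 2/9 | baseline | 1 SD | −0.22 | 9.0% |
| 2/9 | quarter of the change | 1 SD | −0.17 | 7.2% |
| 2/9 | week 1 | 1 SD | −0.11 | 6.1% |
| 1/9 | baseline | 1 SD | −0.11 | 6.0% |
| 2/9 | baseline | 0.5 SD | −0.11 | 5.8% |
| 2/9 in every arm | baseline | 1 SD | 0.00 | 5.0% |
| 2/9, week 2 measured | none | 1 SD | 0.00 | 5.0% |

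In the first row, 8.3 of the 9.0 percentage points favour 1 Hz. The direction reverses if the loss is in 1 Hz.

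**Would a mixed model alone cure this?** With δ = 1.4 and no leavers measured, it gives 1.40 in both cases, so 0.31 too high in B. With half measured it gives 1.41 in A and 1.22 in B (0.13 too high). LOCF with half measured is about 0.31/2 = 0.16 too low in A and correct in B. With no true difference and 20% of 10 Hz lost after session 5, if loss depends on the observed week 1 score the mixed model is unbiased (0.00) and LOCF gives −0.16. If it depends on the unseen week 2 score, the mixed model gives +0.13 and LOCF −0.05. Neither method dominates; measured scores are correct throughout.

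**The case against.** A reader might infer that Research Design and Procedures and Methods contradict each other on early withdrawals. They do not: Research Design is silent on them, so this is a gap. The real mismatch is that one section schedules all outcome measures at weeks 1 and 2 and the other names only the secondary ones. Taken literally, the second would remove the completers' week 1 and week 2 PCL-C as well. It is more likely a drafting slip, since the same section later says "The outcome measures will also be repeated after completion of the Phase 2 group psychotherapy program", which implies earlier administrations. Nor does that wording cause the problem. LOCF alone lets an earlier score stand in; the wording only decides which one.

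Three further points stand in part.

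- The documents do not separate stopping rTMS from leaving the study, and the week 2 assessment is not expressly limited to completers. Some who stop may be measured anyway, but nothing ensures it.
- The 9% case needs one-sided loss, baseline carried and a 1 SD improvement in all arms. The background reports low dropout and very little improvement in Phase 1, and no group therapy runs alongside rTMS, so 1 SD is at the upper end.
- The observed-case analysis is already planned despite its post hoc label. It does not settle the matter, because it fails in case B, where LOCF is right.

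On cost, the PCL-C is routine in the outpatient programme, but no routine administration is described in the break when week 2 falls, so the form has to be added.

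**Conclusion.** The concern holds as a gap in data collection combined with a single-imputation rule on the primary endpoint. The likely bias is small and its sign unknown. Under the assumed 2 of 9 lost from 10 Hz with baseline carried, the error is 0.31 SD if leavers would have improved and zero if they keep no benefit. With no true difference, type I error is about 9% at the upper end and 5% to 7% in the milder cases. All of this rests on assumed losses.

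Two stronger conclusions are not supported. LOCF is not shown to favour either active arm. Nor do these figures show that the primary ANCOVA must give way to a mixed model: without week 2 scores from leavers that is no safer, and with them the ANCOVA is already correct. The case rests on measuring rather than assuming, not on power: in case B, power is 70% with measured scores and 72% with LOCF. The follow-up point is conditional on the LOCF sentence reaching beyond week 2.

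**What to change.** 1. In Procedures and Methods, write: *The primary and secondary outcome measures will be repeated after rTMS sessions 5 and 10, or at termination if a subject withdraws early.*
2. Main fix. Add: *The self-report PCL-C will also be sought at week 2, before Phase 2 begins, from every willing randomised subject, including those who stopped rTMS, and used as the week 2 value in the intent-to-treat ANCOVA.*
3. In Data Analysis, pre-specify the observed-case ANCOVA as a sensitivity analysis for any week 2 values still missing, optionally with a repeated-measures mixed model of weeks 1 and 2. Report by arm how many week 2 values are measured and how many are carried.
4. State that scores from before Phase 2 are not carried to the follow-up visit.

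The cost is some wording and one extra self-report form for the few who stop early. The 3 to 4 week break less 2 weeks of rTMS leaves 1 to 2 weeks to collect it, if rTMS starts promptly. Including the CAPS at termination under item 1 needs the blind evaluator. The intent-to-treat effect may prove smaller than the planned 1.4, leaving power below 80%.
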